after probe insertion with a calibrated micro infusion pump. The probes will then be disconnected from the perfusion pump and left in place with the inlet and outlet tubing capped, which is secured to the leg overnight. The timing of the probe insertion (approximately 12 hr before the resting measurements) is to ensure that the resting measurements are not influenced by the probe insertion [50, 51]. The following morning each subject will undergo the baseline measurement of resting adipose tissue sRAGE collected by the microdialysis probe. The microdialysis probes are perfused with a sterile solution supplemented with 37 g/L dextran-70. Dextran is used to assure there is no net fluid transport across the microdialysis membrane [52, 53]. Therefore, the subjects do not come into contact with the dextran solution. Samples will be collected in sealed microvials that are pre-weighed before and after each collection period to determine actual dialysate weight and calculate dialysate volume. At the start of each microdialysis measurement, each probe is reconnected to the perfusion pump and perfused with sterile water for 10 minutes at 0.3 µl/min and then at 0.3 µl/min for 3 hr while the subjects rest quietly or 4 hrs post-acute aerobic exercise. Subjects will be instructed on how to care for the wound and supplied with ice and pressure bandages after to reduce inflammation and any soreness.

Initial Exercise Bout (moderate treadmill walking)

Upon completion of the baseline testing period, all subjects will be asked to undergo a single, modest treadmill aerobic exercise bout (65% VO₂max for 30 minutes). Prior to this trial, each participant will have been medically cleared for exercise based on screening criteria. This treadmill bout will be supervised by a member of the research team and may be completed at CCRB, Domino Farms, or MCRU (or other appropriate University facility). Participants will be familiarized with the protocol, In addition to intermittent oxygen consumption evaluation, subjects will be fitted with a heart rate monitor to track exercise intensity. Each subject will have a simple blood draw before and after the trial (~80 ml total). This exercise will count as the first exercise training session for subjects randomized to the training group and subjects randomized to the Control group will be advised to resume normal daily activity and standard of care for the duration of the study.

Follow-up Testing

All subjects will return for follow-up testing at approximately weeks 4 and 8. Each subject will have a blood draw (~20 ml) and the AE group will also complete a VO₂max test to adjust target HR for the training protocol.

Final Study Visit Testing

The final study visit at MCRU or Domino Farms will include the same testing procedures for both groups that were completed during baseline testing (i.e., body

composition assessment, cognitive assessment, OGTT, measurement of insulin sensitivity). In addition, all subjects will undergo an acute aerobic exercise bout (treadmill walking) coupled with microdialysis and muscle biopsies.

Total Study Tissue Sampling

Table 1 outlines the approximate amount tissue to be collected during the study. Tissue samples (blood, urine, and muscle) will be obtained during the screening and/or baseline (before the 3 month AE intervention or control period), follow-up visits, and final study visits (after the 3 month AE intervention or control period) time points. Therefore, these time points will be separated by >3 months. In addition, participants in this study will be overweight or obese and have a body weight > 110 lb. Thus, the proposed blood draws are acceptable by University of Michigan IRBMED guidelines.

Table 1		
Time point	Blood	Muscle
Screening Visit		
Both groups	20 ml	-
Baseline Visit		
AE group	280 ml	400 mg
Control group	280 ml	400 mg
Initial Exercise Bout		
AE group	80 ml	-
Control group	80 ml	-
Follow-up Visits		
Both groups	40 ml	-
Final Visit		
AE group	280 ml	400 mg
Control group	280 ml	400 mg
AE group total	~700 ml	~800 mg
Control group total	~700 ml	~800 mg

Sample Preparation, Storage, and Shipping

Study samples and resultant data will not contain personal identifying information. Each subject will receive a unique study identifier and samples will be appropriately labeled based on the testing procedure and sample type. All source document data will be kept in a locked file cabinet and converted to electronic data. All electronic data will be safe-guarded by password protection on a University of Michigan server. Sample preparation will be completed by the research team and/or MCRU/NORC staff during each procedure. This includes processing of muscle biopsy, blood, and microdialysis samples. Samples will be stored in a -80 °C freezer. Handling and shipping of study samples will only occur by the trained research staff as directed by Michigan Occupational Safety and Health Act (MIOSHA) and Occupational Safety and Health Administration (OSHA) guidelines.

Assessment of Safety

The risk to benefit ratio for this study is excellent. Overall, the risks are minor with the information gained on the impact of exercise on diabetes invaluable. Safety will be regularly monitored through personal communication, observation, and documentation. Each individual involved in this study will be encouraged to communicate needs and any potential issues that arise.

Adverse Events

Members of the research team will be present for all components of the study to monitor safety. Additionally, the research team will communicate weekly for review of safety and data collection. In the situation of an adverse event, the event will be immediately managed an IRBMED Adverse Event Report Form will be sent to the appropriate clinical site and Institutional Review Board in a timely manner. This report will include a full description of the event, including the relationship of the incident to the test procedure.

Potential Adverse Events and Mitigation Strategies

Breach of Confidentiality: There is a potential for breach of confidentiality. Study samples and resultant data will not contain personal identifying information. Each sample will be stored with a unique code. All source document data will be kept in a locked file cabinet and converted to electronic data. All electronic data will be safe-guarded by password protection and encryption on a University of Michigan server.

Muscle Biopsy: Risks include discomfort, infection, or excessive bleeding at the biopsy site. These complications will be minimized using sterile techniques and pressure by an experienced team member. Subjects will be instructed that they should report any bleeding or opening of the wound immediately for follow up care. Subjects will be supplied with ice and pressure bandages after each biopsy to reduce inflammation and any soreness after the biopsy. A member of the research team will follow-up with participants the day after each muscle biopsy.

Lidocaine: Lidocaine is a local anesthetic administered during the muscle biopsy technique. It is possible to develop an allergic reaction to lidocaine, which could range from minor itching and a rash to severe respiratory arrest and death. This is a possibility with all medications and we will include subjects in the study only if they are without a history of an allergic reaction. Medical treatment will be provided if an allergic reaction is evident.

Bupivacaine: Bupivacaine is a local anesthetic delivered during the muscle biopsy technique. It is possible to develop an allergic reaction to bupivacaine, which could range from minor itching and a rash to severe respiratory or cardiac arrest and death. This is a possibility with all medications and we will include subjects in the study only if they are without a history of an allergic reaction. Medical treatment will be provided if an allergic reaction is evident.

DEXA: There is a risk of x-ray exposure with DEXA. The duration of each scan will be less than 10 min and the subject will be exposed to a radiation dose of ≤ 0.3 mrem based upon manufacturer's specifications and calculations from Stanford Dosimetry, LLC RADAR Medical Procedure Radiation Dose Calculator. This amount of radiation exposure is considered "general public" exposure by the Nuclear Regulatory Commission.

Blood Samples: Inserting a needle for blood sampling may be associated with some discomfort, bruising, and on a very rare occasion, with inflammation. Strict sterile procedures will be utilized during blood draws to minimize risks.

Urine Collection: There are no known risks to collecting urine samples. However, some people may find it uncomfortable or embarrassing to collect samples.

EKG: Men may need to have a small amount of chest hair shaved off for the ECG pads to stick correctly. A small amount of adhesive might remain on the skin when the pads are removed or the adhesive might pull on hair when removed.

Exercise: There is a risk of physical injury or fatigue due to the cardiorespiratory fitness test and participation in an exercise intervention. However, these risks are generally considered rare and minor. Our investigation team has extensive experience conducting graded exercise tests in a number of special populations (including elderly and diseased populations) and is well versed in how best to minimize risk during these tests. In addition, exercise testing and training will be performed in a facility equipped with AED devices and staff trained in CPR.

Insulin Clamp Procedure: There is a risk that the subject may react to the infusion of glucose or insulin. These reactions could include low blood sugar, an increase in blood pressure, flushing and/or sweating. In the event one of these reactions occur, medical staff will be notified and appropriate measures will be taken.

Heated Hand Box: There is a minor risk of skin discomfort or burn. If the temperature is too warm it can be reduced to improve comfort.

Oral Glucose Tolerance Test: There is a minor potential risk of reaction to the ingestion of glucose. These reactions could include nausea, low blood sugar, an increase in blood pressure, flushing and/or sweating. Continuous blood glucose monitoring will take place during this procedure to provide real time feedback of glucose levels.

Microdialysis: Inserting the microdialysis probes may be uncomfortable or painful.

Study Diet: It may be burdensome for subjects to adhere to a special diet for an extended period of time. The metabolic kitchen staff at MCRU will work to accommodate participant needs.

Unforeseeable Risks: There may be risks or side effects related to the study that are unknown at this time. Continuous monitoring of all participants will facilitate appropriate action in the event of an unforeseeable risk.

Expected Adverse Reactions

There are no expected adverse events.

Serious Adverse Events and Unanticipated Problems

Subjects will be closely monitored by the research team, MCRU, CVC, and/or Domino Farms staff during all testing procedures. Should a serious event occur, it will be managed promptly by the research team and appropriate medical staff.

Abnormal Laboratory Test Values or Abnormal Clinical Finding Procedure

Should an abnormal test value or finding be identified, the subject will be promptly notified and encouraged to communicate the finding with their personal physician.

Reporting Procedures

All adverse events will be reported to the research team for awareness. The study principal investigator, [name] PhD, and a study physician, will ensure the University of Michigan Institutional Review Board is notified within a timely manner.

Safety Oversight

[name], PhD and [name], MD (the physician-of-record) will provide safety oversight for the study. [name], PhD (School of Kinesiology) will serve as our data safety monitor.

STATISTICAL CONSIDERATIONS

Study Hypotheses

Our central hypothesis is that skeletal muscle contributes to sRAGE appearance in the circulation and maintenance of healthy levels of total sRAGE promotes cardiometabolic health. Therefore, two specific working hypotheses have been proposed.

- 1) Skeletal muscle expression of RAGE will decrease following 12-weeks of aerobic exercise training and this change will be related to increases in insulin sensitivity and cardiorespiratory fitness.
- Circulating sRAGE levels will increase following 12-weeks of aerobic exercise training and this change will be related to reduced muscle RAGE expression and increases in insulin sensitivity and cardiorespiratory fitness.

Statistics and Sample Size Considerations

The primary outcomes of this study involve collecting data at pre-aerobic exercise training and 12 weeks of training. Comparisons of trajectories across groups (training vs. Control) over time are made with appropriate adjustments for fixed (age, sex, medications, diabetes duration and severity) and time-varying covariates (i.e., weight, BMI, etc). Because of the anticipated nonlinear response curves of outcome variables we will use nonlinear mixed effects models to analyze our data. Using PROC NLMIXED in SAS 9.2 (SAS Inc.) we will fit the nonlinear models using two likelihood-based methods: adaptive Gaussian guadrature and a first-order Taylor series approximation [54-56]. The nonlinear mixed model is: $y = f(x_{ij}, \beta, u_i) + e_{ij}$, where f is some nonlinear function of known vector covariates (xij) for the jth observation on the jth subject, unknown fixed effect parameters (β), an unknown vector of random effect parameters (u_i), and unknown random errors (eii). For this study, we will treat training group as main fixed effect, intercept as random effects, and all outcomes will be used as responsive variables. Using nonlinear mixed effects models described above, we will reject null hypothesis if significant (p<.05) interaction effect between group and time is observed. Post-hoc analysis will examine differences between groups at different time points to assess the effect of exercise training on the outcome variables across time during the intervention. Our human sample size was determined using data from preliminary studies to provide adequate power after attrition to test the hypothesized effect of training on skeletal muscle RAGE and sRAGE concentrations. We will enroll 75 subjects with the anticipation that there will be 20-25% attrition at 12 weeks. We anticipate that the final N after attrition will be 60 (n= 30 per group). Using the two-sided alpha level of 0.05, we estimate that a total sample size of 60 will enable us to detect a pre-post, between-group difference of 1.24 standard units for RAGE between Aerobic Exercise training and Control groups with a target of 90% statistical power.

Safety and Efficacy Review

Our team has a Michigan Occupational Safety and Health Act (MIOSHA) approved chemical hygiene plan in place. This hygiene plan requires extensive training in the University of Michigan's Responsibility Conduct of Research training program, known as PEERRS (Program for Education and Evaluation in Responsible Research and Scholarship), first aid, and CPR. The research team will be meet weekly to discuss study progress, training, and ensure study objectives and guidelines are met.

Analysis Plan

Due to nature of this study, data will be analyzed on an on-going basis. Participant enrollment will be rolling with sample collection occurring intermittently. Samples will be batched and analyzed as appropriate. Study samples and resultant data will not contain personal identifying information (only a unique study code). All source document data will be kept in a locked file cabinet and converted to electronic data. All electronic data will be safe-guarded by password protection on a University of Michigan server.

QUALITY CONTROL AND QUALITY ASSURANCE

Ethics and Protection of Human Subjects

Coupled with extensive experience testing human subjects in a variety of settings, the training provided by the University of Michigan's Responsibility Conduct of Research training program, known as PEERRS (Program for Education and Evaluation in Responsible Research and Scholarship) will guide the protection of the research team and study participants.

Informed Consent Process

As explained in detail elsewhere, initial screening of participants will occur via a website screening tool or telephone interview. During this time, the study will be described in detail and we will obtain information about age, body mass index (BMI), smoking and physical activity status, current medical conditions, health status and medications. Subjects who meet the initial screening criteria are scheduled for a medical screening. These tests will be performed in the Michigan Clinical Research Unit (MCRU), CVC, Domino Farms, and/or the CCRB (or other University recreation building). Verbal and written informed consent will be obtained during this initial visit according to the guidelines of our Institutional Review Board. Subjects are screened based on the inclusion/exclusion criteria.

Informed Consent/Assent Process (in Case of a Minor)

Minors will not participate in this study.

Subject Confidentiality

The screening process utilized in this study was selected to minimize study risk. All conversations between the research team and participants are considered confidential. Screening will take place in a private environment with only the research team and/or Michigan Clinical Research Unit (MCRU), CVC, or Domino Farms staff present. Study samples and resultant data will not contain personal identifying information. All source document data will be kept in a locked file cabinet and converted to electronic data. All electronic data will be safe-guarded by password protection on a University of Michigan server.

Study Discontinuation

Participants are free to withdraw their consent and discontinue participation at any time. We do not anticipate participant withdrawal due to study-related reasons as similar exercise training interventions have been taking place for decades with high levels of success. Additionally, we have experience managing clinical trials in the proposed population [26, 30, 34, 35]. However, we recognize participants interests, health and schedules may change. The research team's best effort will be made to accommodate the participants needs and minimize attrition.

Future Use of Stored Specimens

Participants will be asked to consent for future use of their samples. We expect that the data and tissue and blood samples obtained from the proposed study will have lasting research value to maximize productivity for the research team. We intend to use these resources to explore future mechanisms and the data obtained that can be mined for new and impactful opportunities.

DATA HANDLING AND RECORD KEEPING

Data Management Responsibilities

Data will be managed internally by the research team. Source study documents will be converted to electronic files as needed and interpreted by the research team on an on-going basis. The source study documents will be safe-guarded in a locked file cabinet. Weekly study team meetings will address data management needs.

Data Collection Process

Data collection will be conducted by the research team, MCRU, CVC, and/or Domino Farms staff at the University of Michigan. Specifically designed protocol documentation forms will guide the data collection process.

Study Records Retention

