Figure 2 provides a general framework of the study design. This 12-week clinical study involves the testing and training of middle age to older (40 - 75 y), overweight or obese adults (BMI 26 - 44 kg/m²) with type 2 diabetes (T2DM). Sixty subjects will be randomized to 12 weeks of aerobic exercise training plus standard care (Aerobic Exercise group; n=30) or standard care only (Control group; n=30). Subjects randomized to the Control group will be given the option of an off-label exercise intervention. Therefore, Control group participants will be allowed to enroll in the AE training group after completion of the original Control group trial period. All subjects will undergo the same baseline and post testing for basal metabolic rate, maximal aerobic capacity (VO₂max), body composition, insulin sensitivity, and microdialysis sampling coupled with muscle biopsies during an acute aerobic exercise trial before.

Due to the complexity of this study, an interdisciplinary research team with experience in clinical trials, pathophysiology of, and research in obesity, insulin resistance and T2DM, vascular function, aerobic exercise testing/training, clinical medicine, biotechnology, and advanced biostatistics has been assembled. The research staff has many years (>10 y) of direct research experience with human subjects and have been trained by experts in the field and University of Michigan protocols and guidelines.

Primary Outcome Measure

1) Quantify the change in basal circulating sRAGE after 12-weeks of supervised aerobic exercise training.

Serum will be separated from blood samples collected in vacutainer tubes via centrifugation before and after 12-weeks of aerobic exercise training. sRAGE will be quantified in these serum samples via ELISA (Quantikine, Human RAGE Immunoassay) per manufacture's protocol.

Secondary Outcome Measures

1) Quantify the change in basal muscle RAGE expression after 12-weeks of supervised aerobic exercise training.

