Basal biopsy derived skeletal muscle RAGE expression will be determined from the vastus lateralis before and after 12-weeks of aerobic exercise training. RAGE expression will be quantified via Western Blot. Muscle samples (~10 mg) will be homogenized and protein concentration will be determined via BCA assay (Pierce). Samples (20 µg protein) will be diluted in SDS buffer, heated at 85 °C for 5 min, resolved via SDS-PAGE (Bio-Rad Laboratories, Hercules, CA) and transferred to a nitrocellulose or PVDF membrane. Blocking will occur for 1 h and primary antibody (RAGE; Abcam, Cambridge, MA) incubation will occur overnight at 4 °C and quantified vs a standard or total protein.

2) Quantify the change in aerobic capacity (VO₂max) after 12-weeks of supervised aerobic exercise training.

Maximal oxygen consumption (VO₂max) will be established via indirect calorimetry during an incremental treadmill test (Cornell protocol) before and after 12-weeks of aerobic exercise training. Criteria, such as, rating of perceived exertion >18, respiratory exchange ratio >1.10, no further increase in VO₂ despite increasing workloads, heart rate greater than age-predicted maximum, or volitional fatigue will be used to indicate a successful VO₂max was achieved.

3) Quantify the change in insulin sensitivity after 12-weeks of supervised aerobic exercise training.

Insulin sensitivity will be established via hyperinsulinemic-euglycemic clamp before and after 12-weeks of aerobic exercise training. After the initial basal period of this procedure, a primed-continuous infusion (40mU/m²/min) of human insulin will be initiated and maintained for a period of 120 min. Glucose levels will be clamped at 90 mg/dL by use of a variable glucose infusion (20% dextrose). Blood glucose will be measured every 5 min to monitor levels and used to adjust the variable glucose infusion rate. The clamp procedure will be completed after the 120-min period of hyperinsulinemia or until steady state glucose concentration is achieved.

ELLIGIBILITY AND ENROLLMENT

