Group Assignment Procedure

Following enrollment into the study, participants will be randomized into either the Aerobic Exercise group (n=30) or Control group (n=30. Females and males will be equally distributed between the groups. Regardless of group assignment, each participant will receive standard care for diabetes management.

Aerobic Exercise Training

Every AE training session will be supervised by the research team using established protocols [22-28]. Training sessions will take place at the Central Campus Recreation Building (CCRB), Domino Farms, or other University of Michigan recreation facility (e.g., North Campus Recreation Building) approximately 5 days per week and include treadmill walking, cycling, elliptical, or other related modes of exercise. Briefly, AE training will begin with a 2-week ramp-up, familiarization period of progressing exercise intensity and duration. Training intensity will progress from 55% VO₂max for week 1 (40 min session), to 60-65% VO₂max for week 2 (50 min session), to ~70% VO₂max for all other weeks (50 min session). Subjects will perform a brief warm-up and cool-down (~5 min each) that may include stretching or other light exercises for a total exercise time of 60 min. Subjects will wear heart rate monitors during each training session to provide real-time feedback of target heart rate. Intensity, duration, resting and exercise heart rates, and blood pressures will be recorded for each session. Exercise duration and intensity may be adjusted at the discretion of the PI, Co-I, or study team member. Followup VO₂max tests will be performed at approximately weeks 4 and 8 to monitor progress. AE intensity will be adjusted to match the prescribed training intensity [23, 24, 29-32]. Subjects in the AE training group will also conduct foot safety checks with the research team to monitor foot ulcers/blisters. Relevant findings during foot inspections will be addressed with the participant and study physician. Non-weight bearing exercise may be implemented if the subject is limited.

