- Apply pressure to incision site with sterile gauze until bleeding stops (or is very light)
- While pressure is being applied to the thigh, the biopsy assistant attaches a 3-way stopcock to a 60cc or similar syringe
- One end of sterile pressure tubing is attached to the sterilized biopsy needle (4-5g Bergstrom or UCH biopsy needle), and the other end of the tubing is handed to the assistant to attach to their 3-way stopcock to syringe (or similar) set-up for suction
- The biopsy needle is inserted into the incision with firm pressure, the biopsy needle is inserted past the fascia, in the location/direction of the applied anesthetic
- Once the biopsy needle is fully inserted, the biopsy assistant pulls back firmly on the plunger of the syringe to apply steady suction

- The sample is collected by closure of the biopsy needle To increase sample yield, the biopsy needle can be quickly rotated then opened and closed 3-5 times to obtain a few "snips" of sample before removing the biopsy needle from the thigh
- The sample is placed on a sterile absorbent pad, and pressure is applied to the biopsy site with sterile gauze
- The biopsy assistant quickly rinses/cleans the sample and gently dabs the sample on the absorbent pad to remove excess liquid
- The sample is processed according to PI discretion
- While research team member is cleaning and storing the sample, manual pressure is applied to the incision site
- The biopsy procedure can be repeated in the same incision site (or separate preprepared site) if more tissue is needed
- When the entire biopsy procedure is finished, firm direct pressure is applied to the incision site until bleeding stops (~10 minutes)
- Incision site is cleaned with 70% ethanol and dried with sterile gauze
- The incision is closed with steri-strips or equivalent and an overlaying transparent dressing
- A pressure dressing is applied to the thigh until bedtime the night of the biopsy procedure
- Participant is instructed to avoid water submersion for 3 days and to keep the bandages on for 3-5 days

Upon discharge, provide participant with pre-printed post-procedure care instructions with emergency contact information.

Acute Aerobic Exercise Bout: Treadmill Walking

[figure not shown]

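### The muscle RAGE blot has no fixed denominator, and the plan describes no masking of its reading to arm or visit

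*Combined protocol and SAP*

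**What the plan says.** All references are to the combined protocol and SAP.

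- **Endpoint.** Item 1 under Secondary Outcome Measures is "Quantify the change in basal muscle RAGE expression after 12-weeks of supervised aerobic exercise training". Muscle RAGE is also the second study objective and one of the two working hypotheses, which predict a fall with training.
- **Assay.** The same item fixes a BCA protein assay and a 20 µg protein load per sample. It leaves two choices open: proteins are "transferred to a nitrocellulose or PVDF membrane", and the RAGE signal is "quantified vs a standard or total protein". It gives no rule for choosing, for replicate or repeat blots, or for placing a participant's two visits on one gel. The Skeletal Muscle Biopsy Procedure adds "The sample is processed according to PI discretion".
- **Labelling.** Sample Preparation, Storage, and Shipping states "Each subject will receive a unique study identifier and samples will be appropriately labeled based on the testing procedure and sample type". That section and the Analysis Plan present the code as a way of removing personal identifiers.
- **People.** Under Aerobic Exercise Training, "Every AE training session will be supervised by the research team using established protocols". On handling, "Sample preparation will be completed by the research team and/or MCRU/NORC staff during each procedure". Data Management Responsibilities says "Source study documents will be converted to electronic files as needed and interpreted by the research team on an on-going basis", and the Analysis Plan has data analysed while enrolment is still rolling.
- **Masking.** No section mentions masking of laboratory staff, outcome assessors or analysts.

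**The concern.** Participants and trainers necessarily know the allocation. In such a trial, protection against assessment bias has to come from the assay and analysis stages. Densitometry involves judgement on exposure, band boundaries, background and which blots to repeat, and here the denominator is open as well. The hypotheses tell any reader which direction to expect.

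The endpoint carries more weight than its secondary label suggests. The sRAGE hypothesis predicts that the rise in sRAGE will be related to reduced muscle RAGE, so a distorted blot value would affect that analysis too. The sample-size text says the study was sized for both muscle RAGE and sRAGE.

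**Working it through.** **1. The plan's own figure.** The only number that may be tied to this endpoint is in Statistics and Sample Size Considerations: 60 participants (30 per group) to detect 1.24 standard units for RAGE with 90% power at two-sided 0.05. Reading 1.24 as SDs of the change score:

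n per arm = 2 × (1.960 + 1.282)² / 1.24² = 2 × 10.51 / 1.538 = 13.7, so 14 (15 by t-test).

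This does not reproduce 30. It comes close (29 per arm by t-test) only if the unit is a single-visit SD and the pre-post correlation is zero, which the plan does not state. That is a separate matter and neither supports nor weakens this point. The plan gives no figure for blot reproducibility, reader agreement or agreement between the two denominators.

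**2. What the documents settle about reading.**

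| Question | Answer in the documents |
|---|---|
| Which denominator? | Either of two, no rule |
| Who reads the blots? | Not stated |
| Who holds the code key? | Not stated |
| Do labels show arm? | Arm is not among the listed label items |
| Do labels show visit? | Not stated |
| Is the reader kept from the allocation? | Not stated |
| Are values locked before linkage to arm? | Not stated; analysis is ongoing |

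The outcome, sample-handling, statistics and data-management sections are all present in the text, so these gaps are not explained by removed pages.

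**3. How a reading bias would act.** Suppose the reader shades post-intervention values in the exercise arm down by δ. The group-by-time contrast becomes

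[(post − δ) − pre] in exercise − [post − pre] in control = true contrast − δ.

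The whole of δ enters the estimate, and a larger sample does not dilute it. If the reader knows visit but not arm and shades both arms equally, δ cancels in this contrast. It would still distort the within-group change and its relation to other changes. Both arm and visit therefore need hiding. The documents give no basis for a value of δ.

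**4. What the open denominator would permit, as a hypothetical.** Assume both versions are tested at two-sided 0.05, the better is reported, there is no true effect, and the two test statistics are bivariate normal with correlation r. Then

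P(false positive) = 1 − P(|Z₁| ≤ 1.96 and |Z₂| ≤ 1.96).

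For independent tests this is 1 − 0.95² = 0.0975. For correlated tests:

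| r (assumed) | Either test significant, two-sided (nominal 5%) | Significant in the favoured direction (nominal 2.5%) |
|---|---|---|
| 0.5 | 9.1% | 4.5% |
| 0.7 | 8.3% | 4.2% |
| 0.8 | 7.8% | 3.9% |
| 0.9 | 7.0% | 3.5% |
| 0.95 | 6.5% | 3.2% |

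The documents give no r. Every sample is loaded at 20 µg, so both denominators correct mainly the residual loading error. The lower rows are therefore the more plausible.

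**The case against.** A reader might infer that the blots are read by the same unmasked people who train the participants, and that those people know which code belongs to which arm. The documents do not support either statement. The blot reader is never named. The research team is described as interdisciplinary, with exercise training, biotechnology and biostatistics among its areas, so one collective label does not show that the trainer and the densitometry reader are the same person. Sample preparation may be done by clinical-unit or nutrition-centre staff, and it concerns processing at collection. The sentence on ongoing interpretation concerns source documents and does not mention blots. Silence about the key is not evidence that readers know the arm.

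The open denominator can also be read innocently, as one method to be chosen once when the assay is set up. No section says both will be computed and the better one reported. Equal loading makes close agreement likely, and the outcome is secondary: the primary is a serum ELISA run to the manufacturer's protocol.

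All of this stands, and it limits the finding to what is unspecified. It does not remove the finding. A per-subject confidentiality code is not masking unless the reader is also kept from the key and from visit labels, and the plan says neither.

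**Conclusion.** The point holds as a gap in safeguards. The denominator for muscle RAGE is open, and no masking of blot reading to arm or visit is described. Samples are coded, but the reader and key holder are not stated, and the team that supervises training also interprets data as they accrue. Biased reading is a possibility that the plan does not close off; nothing in the documents shows it occurring.

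The size of any reading bias cannot be calculated from the documents. The range of about 6.5% to 9.1% against 5% is hypothetical. It requires that both denominators be tested and the better result reported, and it rests on assumed correlations of 0.95 to 0.5. It should not be quoted as the trial's error rate.

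The open denominator alone would be little more than a missing detail. Together with the absence of masking for a judgement-dependent endpoint in an open-label trial, it justifies a change that should be made, mainly because the change is cheap and masking cannot be restored once blots have been read with knowledge of arm or visit.

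**What to change.** Before any blot is run:

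1. Name one denominator for all muscle RAGE blots, and report the other only as a sensitivity analysis.
2. Have an existing team or MCRU member who does not read blots relabel the muscle aliquots with random codes that hide arm and visit. That person keeps a pairing list so that each participant's pre and post samples run on the same gel, with lane order following the random code so that position does not reveal visit.
3. State who reads the blots and who holds the key, and that the reader has no access to it.
4. Lock the densitometry values before the codes are linked to arm and visit.

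Extending the recoding to the serum sRAGE ELISA is optional; that assay leaves less to the reader's judgement.

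The cost is a relabelling list, a pairing list, some handling time and a few sentences in the protocol, using existing staff and samples. The trade-off is that no arm-level blot results are available until values are locked, which restricts the ongoing analysis for this endpoint. Sample size, visits and participant procedures do not change.
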